### 9.6.3 Exploratory Efficacy Analysis

The following exploratory analyses will be further described in the SAP:

- ORR by RECIST v1.1 as assessed by the investigator in exploratory Cohort A2
- ORR by RECIST v1.1 and GCIC CA-125 criteria in exploratory Cohort A2
- PFS in exploratory Cohort A2
- DOR in exploratory Cohort A2
- Explore mutations in BRCA1, BRCA2, other HRR genes as molecular markers of efficacy
- Explore PD-L1 expression as a molecular marker of efficacy
- Explore LOH, TMB, and other genomic and transcriptional signatures as molecular markers of efficacy

## 9.7 ctDNA and immunogenicity Analyses

Tumor tissue, plasma, and blood specimens will be used for exploratory biomarker analyses in an effort to understand the association of these markers with clinical activity or resistance to rucaparib and/or nivolumab, including efficacy and/or adverse events.

## 9.8 Safety Analyses

All safety analyses will be summarized by cohort.

Safety endpoints are incidence of AEs, clinical laboratory abnormalities, and dose modifications.

Data from all patients who receive at least 1 dose of any study drug will be included in the safety analyses. AEs, clinical laboratory results, vital signs, ECG results, , and concomitant medications/ procedures will be tabulated and summarized.

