The sponsor has initiated a Phase 3 study (Study CO-338-087 [ATHENA]) to evaluate the combination of rucaparib and nivolumab in newly diagnosed patients with advanced ovarian cancer as switch maintenance in women who have had a response to first-line platinum-based chemotherapy. Rucaparib and nivolumab are being administered at the same dose and regimen as proposed in the current protocol. Further, establishment of baseline laboratory values for each patient in Cohorts A1 and A2, following monotherapy oral drug and prior to beginning the combination therapy will help guide AE management during administration of the oral/IV combination therapy. The design is described in [Section 3.1](#), and the analysis is described in [Section 9.10](#).

Please see [Section 5.5](#) regarding appropriate dose modifications of the study drugs.

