### 2.2 Secondary Objectives

The secondary objectives of this study, using the same comparisons as the primary objective, are:

- To evaluate the ORR by RECIST v1.1 and Gynecologic Cancer InterGroup (GCIG) cancer antigen 125 (CA-125) criteria (*Cohort A1 only*)
- To evaluate the ORR by RECIST v1.1 as assessed by the investigator, according to molecularly-defined HRD subgroups: BRCAwt/LOHhigh; BRCAwt/LOHlow; BRCAwt/LOHunknown; and sBRCA (*Cohort A1 only*)
- To estimate PFS (*Cohort A1 only*)
- To evaluate DOR (*Cohort A1 only*)
- To evaluate safety and tolerability of rucaparib in combination with nivolumab

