### 3.1.2 Treatment Phase

The first dose of oral study treatment will be administered on Day 1 of Cycle 1 and continue BID throughout the cycle as monotherapy. Oral study drug administration will begin 28 days (1 cycle) prior to IV study drug administration to explore the hypothesis that immune priming of the tumor microenvironment with monotherapy rucaparib will enhance the activity in combination with nivolumab. Within 5 days and prior to commencement of IV nivolumab treatment on Cycle 2 Day 1 (= Cycle 1 Day 28 [window: -5 days]), collection of a primary or metastatic tumor sample is mandatory, unless tumor biopsy procedure is contraindicated (eg, unacceptable risk in the opinion of the investigator). The tumor sample will be analyzed by the central laboratory to assess molecular markers of efficacy or resistance, as well as the effect of rucaparib on the immune microenvironment. Administration of IV study drug will begin on Day 1 of Cycle 2. Details on study drug administration are described in [Section 5.4](#).

Patients will come into the study site for a visit on Day 1 and Day 15 of Cycles 1 and 2, and on Day 1 of every cycle thereafter. A blood sample will be collected from all patients at Cycle 1 Day 1 and stored for subsequent genomic DNA testing and determination of germline status.

Study treatment will continue in 28-day cycles until 24 months from the start of the oral/IV combination treatment (ie, 25 months ), disease progression, or unacceptable toxicity, whichever occurs first. Patients will undergo procedures and assessments, including regular safety, PK, and efficacy evaluations, during the entire conduct of the study.

Tumor assessments by CT scan will be performed every 8 calendar weeks ( $\pm 7$  days) from the start of the oral/IV combination treatment on Cycle 2 Day 1, up to 18 months and then every 12 calendar weeks ( $\pm 7$  days) thereafter and at the End of Treatment Visit, if applicable, until confirmed objective radiological disease progression, as assessed by the investigator. Tumor assessments are to be performed prior to the next scheduled IV nivolumab treatment.

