Bilirubin must be within normal limits and alkaline phosphatase must be < 3 x ULN. Monitor liver function tests weekly. If the patient has Grade 3 ALT/AST and continues on oral study drug, and levels do not decline within 2 weeks or they continue to rise, treatment interruption and improvement to ≤ Grade 2 will be required before oral study drug can be resumed, either at the current dose or at a reduced dose.

Monitor liver function tests weekly for 3 weeks after oral study drug has been restarted.

Grade 2 for nivolumab is described as ≥ 1.5 x baseline and baseline is the day the combination treatment starts (ie, Cycle 2 Day 1 in Cohort A1 and A2).

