## 9 PLANNED STATISTICAL METHODS

### 9.1 General Considerations

All safety analyses will be summarized for all patients who received at least 1 full or partial dose of protocol-specified treatment. Efficacy will be summarized for all treated patients according to the intent-to-treat principle. Cohorts A1 and A2 will be summarized separately for all safety and efficacy analyses.

Quantitative variables will typically be summarized using frequencies and percentages for appropriate categorizations and may also be summarized using descriptive statistics. For variables summarized with descriptive statistics, the following will be presented: N, mean, standard deviation (StD), median, minimum, and maximum. Categorical variables will be presented using frequencies and percentages.

The Kaplan-Meier methodology will be used to summarize time-to-event variables. If estimable, median (50th percentile) with the 95% confidence interval (CI) will be summarized. The number of patients with events and the number of censored patients will also be presented.

All data will be used to their maximum possible extent but without any imputations for missing data. Unless otherwise specified, baseline is defined as the last measurement on or prior to the first day of study drug administration.

All statistical analyses will be conducted with the statistical analysis software (SAS®) System, Version 9.3 or higher. Further details around the statistical analyses planned in this study will be outlined in the Statistical Analysis Plan (SAP).

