## 9.3 Analysis Populations

**Safety Population:** The Safety Population will consist of all patients who received at least 1 full or partial dose of any protocol-specified treatment.

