### 9.8.1 Adverse Events

Adverse events will be classified using the Medical Dictionary for Regulatory Activities (MedDRA) classification system. The severity of the toxicities will be graded according to the NCI CTCAE v5 or later. Only TEAEs will be collected: TEAEs are defined as AEs with onset

date on or after the date of first dose of study drug until 28 days after the last dose of oral study drug or 100 days after the last dose of IV study drug, whichever occurs later.

The number and percentage of patients who experienced TEAEs for each system organ class (SOC) and preferred term will be presented. Multiple instances of the TEAE in each SOC and multiple occurrences of the same preferred term are counted for the worst only once per patient. The number and percentage of patients with at least one TEAE will also be summarized.

Tables for TEAEs and treatment-related TEAEs will be presented as follows but are not limited to:

- All;
- By CTCAE grade;
- Grade 3 or greater;
- Serious;
- TEAEs with an outcome of death;
- TEAEs leading to discontinuation of study drug;
- TEAEs resulting in interruption/delay of study drug; and
- TEAEs resulting in dose reduction of study drug.

The incidence of TEAEs will be summarized by relationship to study drug according to the following categories: “treatment-related,” or “not treatment-related”. If a patient experiences multiple occurrences of the same AE with different relationship categories, the patient will be counted once, as a relationship category of treatment related.

If a patient experiences multiple occurrences of the same AE with different toxicity grades, the patient will be counted once for the maximum (most severe) toxicity grade. AEs with a missing toxicity grade will be presented in the summary table with a toxicity grade of “Missing.” For each toxicity grade, the number and percentage of patients with at least 1 TEAE of the given grade will be summarized.

The time to the first TEAE and first treatment-related TEAE that results in a dose reduction, delay, interruption or discontinuation of study drug is defined as 1+ the number of days from the first dose of study drug to the start of the first adverse event. The cumulative incidence is presented in a 1-KM graph for just the patients with an event and the median time to onset will be calculated together with the 95% CI.

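### Safety of the combination is a stated objective, but Section 9.8 prespecifies no summary that separates the rucaparib-only run-in from the period on nivolumab

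*Combined protocol and SAP*

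**What the plan says.** Section 2.2 lists the objective, for both cohorts: "To evaluate safety and tolerability of rucaparib in combination with nivolumab". Section 3.1.2 sets the sequence of the two drugs: "Oral study drug administration will begin 28 days (1 cycle) prior to IV study drug administration".

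Section 9 then fixes the safety analysis as follows.

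- **Population.** Section 9.3: "The Safety Population will consist of all patients who received at least 1 full or partial dose of any protocol-specified treatment". Section 9.8 repeats this: "Data from all patients who receive at least 1 dose of any study drug will be included in the safety analyses". No nivolumab-treated set is defined.
- **Windows.** Treatment-emergent events (9.8.1) and the laboratory and vital-sign on-treatment periods (9.8.2, 9.8.3) open at the first dose of study drug, which is rucaparib on Cycle 1 Day 1.
- **Time to first event.** For events leading to dose modification, 9.8.1 counts "the number of days from the first dose of study drug to the start of the first adverse event", plus one.
- **Baseline.** Section 9.1: "baseline is defined as the last measurement on or prior to the first day of study drug administration". That sentence opens with a proviso allowing a different baseline to be specified; Section 9.8 specifies none.
- **Counting.** A patient with repeated occurrences of an event counts once, at the worst grade. Laboratory shift tables compare the baseline grade with the highest, lowest and final on-treatment grade.
- **Split.** By cohort only. Relationship is tabulated as related or not, without naming the drug.

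Elsewhere the protocol does use a reference point after the run-in. Section 1.2.2 refers to "establishment of baseline laboratory values for each patient in Cohorts A1 and A2, following monotherapy oral drug and prior to beginning the combination therapy" and gives its purpose as guiding adverse-event management. For nivolumab creatinine grading, Table 4 footnote 11 states that "baseline is the day the combination treatment starts".

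**The concern.** The objective concerns two drugs given together, while the planned summaries begin a cycle before the second drug is given. Section 1.1.2.3.3 describes ALT/AST and creatinine rises and anemia as common on rucaparib alone, so such events can be expected in Cycle 1. In the planned tables they fall in the same cell as events that start after nivolumab is added. In a single-arm study, the run-in is the only within-patient reference for what changed at that point. Without a prespecified split, a reader of the summary tables cannot see how much of a reported rate arose on both drugs, and a split chosen after the data are seen would carry less weight.

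**Working it through.** **Inputs from the documents.** Run-in of 28 days (3.1.2), with a visit window of ±3 days (7.1 and Table 6 footnote a), so the offset is nominal. Maximum denominators of 43 in Cohort A1 and 10 in Cohort A2 (4.1). Up to 24 months of combination treatment, given as 25 months in total (3.1.2).

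**Not in the documents, so assumed.** The number of patients who never receive nivolumab: k = 1 to 6 of 43, and 1 to 2 of 10. Event risks in each period: 10% to 30% in the run-in and 20% on the combination.

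**1. The plan's own figure.** With a month of 365.25/12 = 30.44 days, 24 months + 28 days = 730.5 + 28 = 758.5 days = 24.9 months. The stated 25 months is reproduced, so the run-in is inside the planned safety window.

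**2. Share of treatment time spent in the run-in.** 28 ÷ total days on treatment:

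| Patient stops at | Calculation | Share |
|---|---|---|
| First scan, Cycle 4 Day 1 | 28/84 | 33% |
| 16 weeks | 28/112 | 25% |
| 12 months | 28/365.25 | 7.7% |
| Maximum | 28/758.5 | 3.7% |

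The run-in weighs most for patients who stop early.

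**3. Merging, even if every patient reaches nivolumab.** With independent risks p_r (run-in) and p_c (combination), the once-per-patient rate is 1 − (1 − p_r)(1 − p_c). With p_c = 20%:

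- p_r = 10%: 1 − 0.90 × 0.80 = 28%
- p_r = 20%: 1 − 0.80 × 0.80 = 36%
- p_r = 30%: 1 − 0.70 × 0.80 = 44%

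Each is a correct whole-regimen rate, but none is the 20% that arose on the combination. In the middle case, 0.20 × 0.20 = 4% of patients have the event in both periods and appear once.

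**4. Masking under the stated rules.**

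- *Worst grade.* A Grade 2 ALT rise in Cycle 1 that resolves and recurs at Grade 2 in Cycle 4 is one Grade 2 patient. The recurrence is invisible in the table. Only a recurrence at a higher grade would show.
- *First event.* A dose-modifying event in the run-in ends the time-to-first-event analysis for that patient, so a later event on the combination does not enter.
- *Shift to maximum.* Creatinine at Grade 0 before Cycle 1, Grade 2 by Cycle 2 Day 1 and stable afterwards reads 0 to 2. Creatinine at Grade 0 until nivolumab starts and Grade 2 afterwards also reads 0 to 2. From the last pre-nivolumab value, the two read 2 to 2 and 0 to 2.

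**5. Dilution by patients never given nivolumab.** Shown rate = true rate × (N − k)/N. For an event seen only with nivolumab, at a true 20% of exposed patients:

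| N | k | Calculation | Shown |
|---|---|---|---|
| 43 | 1 | 20% × 42/43 | 19.5% |
| 43 | 4 | 20% × 39/43 | 18.1% |
| 43 | 6 | 20% × 37/43 | 17.2% |
| 10 | 1 | 20% × 9/10 | 18% |
| 10 | 2 | 20% × 8/10 | 16% |

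As counts, with k = 5: 4/43 = 9.3% (exact 95% interval 2.6% to 22.1%) against 4/38 = 10.5% (2.9% to 24.8%). The difference of 1.2 points is small beside either interval.

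**The case against.** The run-in is a deliberate part of the regimen, so counting everyone dosed from the first dose is the right summary of the regimen's tolerability, including patients who cannot get through Cycle 1. That stands, and those tables should stay.

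The text is also not closed. The baseline sentence carries its proviso, the list of adverse-event tables in 9.8.1 is open-ended, and 9.1 leaves further detail to an SAP. A split is therefore permitted, but it is not prespecified.

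Some period information would survive. The onset curve in 9.8.1 shows dose-modifying events before about Day 28, and by-patient listings are planned. Neither gives rates with the right denominator for adverse events in general.

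Three stronger readings are tempting, and the documents support none of them:

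- *That run-in events will be labelled as combination safety.* No table carries that title; 9.8.2 and 9.8.3 speak of an on-treatment period.
- *That the protocol contradicts itself on baseline.* The Cycle 2 Day 1 reference in 1.2.2, Table 4 footnote 11 and the renal algorithm in Appendix 6 serves adverse-event management, and the last two concern creatinine only. None sets an analysis baseline.
- *That onset of nivolumab-caused events is overstated by at least 28 days in every patient.* The visit window allows nivolumab to start slightly earlier, and no onset analysis specific to nivolumab is planned.

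**Conclusion.** The point holds as a gap in prespecification. For a stated secondary objective, Section 9.8 offers only whole-regimen summaries, and its counting, first-event and shift rules prevent those tables from showing what arose after nivolumab began. Merging and masking are the main problem and do not depend on dropouts. Their size rests on period-specific event rates that the documents do not give, so the 28% to 44% range is illustrative and assumes independence between periods. Dilution is minor: under 3 percentage points on a 20% rate in Cohort A1, for up to 6 of 43 assumed never exposed.

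The windows are explicit for adverse events, laboratory values and vital signs. For ECGs and concomitant medications only the all-dosed population is stated. The primary response-rate analysis is unaffected.

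**What to change.** In Section 9.8, keep the all-dosed tables as the whole-regimen summary and prespecify three supplementary sets:

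1. Treatment-emergent events by onset or worsening before, versus on or after, the first nivolumab dose, with nivolumab-treated patients as denominator for the second period.
2. Laboratory shift tables for the combination period, taking the last value before first nivolumab as baseline, shown beside the shifts from the pre-Cycle 1 baseline.
3. Time to first dose-modifying event counted from the first nivolumab dose.

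Report both sets when describing combination safety. Using the split tables alone would drop patients who stopped in Cycle 1 and hide rucaparib abnormalities that persist.

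The cost is analysis wording and a few tables. Event onset is recorded (8.8.1), and hematology and chemistry are already drawn at Cycle 2 Day 1 (7.4.4), so visits, sample size and the primary analysis do not change. There are limits to state with the results. The second-period denominator is smaller and selected for having tolerated Cycle 1. The periods differ greatly in length, and rucaparib continues through both. The before/after contrast is therefore descriptive and cannot isolate an effect of nivolumab.

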### 9.8.1 Adverse Events

Adverse events will be classified using the Medical Dictionary for Regulatory Activities (MedDRA) classification system. The severity of the toxicities will be graded according to the NCI CTCAE v5 or later. Only TEAEs will be collected: TEAEs are defined as AEs with onset

date on or after the date of first dose of study drug until 28 days after the last dose of oral study drug or 100 days after the last dose of IV study drug, whichever occurs later.

The number and percentage of patients who experienced TEAEs for each system organ class (SOC) and preferred term will be presented. Multiple instances of the TEAE in each SOC and multiple occurrences of the same preferred term are counted for the worst only once per patient. The number and percentage of patients with at least one TEAE will also be summarized.

Tables for TEAEs and treatment-related TEAEs will be presented as follows but are not limited to:

- All;
- By CTCAE grade;
- Grade 3 or greater;
- Serious;
- TEAEs with an outcome of death;
- TEAEs leading to discontinuation of study drug;
- TEAEs resulting in interruption/delay of study drug; and
- TEAEs resulting in dose reduction of study drug.

The incidence of TEAEs will be summarized by relationship to study drug according to the following categories: “treatment-related,” or “not treatment-related”. If a patient experiences multiple occurrences of the same AE with different relationship categories, the patient will be counted once, as a relationship category of treatment related.

If a patient experiences multiple occurrences of the same AE with different toxicity grades, the patient will be counted once for the maximum (most severe) toxicity grade. AEs with a missing toxicity grade will be presented in the summary table with a toxicity grade of “Missing.” For each toxicity grade, the number and percentage of patients with at least 1 TEAE of the given grade will be summarized.

The time to the first TEAE and first treatment-related TEAE that results in a dose reduction, delay, interruption or discontinuation of study drug is defined as 1+ the number of days from the first dose of study drug to the start of the first adverse event. The cumulative incidence is presented in a 1-KM graph for just the patients with an event and the median time to onset will be calculated together with the 95% CI.

Non-TEAEs (pre-treatment and post-treatment) will be presented in the by patient data listings for the safety population. MedDRA PTs were combined for the following similar terms

- Asthenia/Fatigue
- Alanine Aminotransferase (ALT)/ Aspartate Aminotransferase (AST) Increased

- Anaemia and/or Low/Decreased Haemoglobin
- Thrombocytopenia and/or Low/Decreased Platelets
- Neutropenia and/or Low/Decreased Absolute Neutrophil Count (ANC)

In addition, the analysis of combined terms for anemia is explored as a time to first event analysis as described above. Transfusions (blood or plasma) and concomitant medications/growth factor support received for cytopenias are provided in patient listings.

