- g = A complete physical exam should be performed at Screening and End of Treatment Visits; a limited physical exam may be performed at all other visits. Height at screening only.
- h = To be performed ≤ 14 days prior to the first dose of rucaparib. Serum pregnancy test to be performed ≤ 3 days prior to the first dose of rucaparib, if applicable.
- i = Vital signs (blood pressure, pulse, and temperature) to be taken on clinic visit days, after the patient has been resting for at least 5 minutes.
- j = AEs (inclusive of SAEs and AESIs) occurring after first dose of rucaparib through 28 days after last dose of rucaparib will be recorded. In addition, SAEs occurring after signing of the ICF and that were related to a screening procedure will also be reported. Ongoing SAEs, AESIs, and treatment-related Grade 3/4 AEs will be followed to resolution or stabilization, death, or until lost to follow-up. Only related SAEs and AESIs (regardless of causality) will be reported after the 28-day Follow-up Visit.

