#### 7.5.4 Safety Evaluations

##### 7.5.4.1 Adverse Event Assessment

The investigator has the responsibility for assessing the safety of the patients and for compliance with the protocol to ensure study integrity. During the screening period, unless otherwise required by local regulations, SAEs which are related to protocol-mandated assessments will be reported. Once enrolled and study drug is administered, patients will be monitored for all AEs/SAEs/AESIs during study participation and until 28 days after the last dose of study drug and 100 days after the last dose of IV study drug, whichever occurs later. After the 28-day (oral and/or IV, whichever occurs later) or 100-day (IV) window, only study drug-related SAEs and all AESIs, irrespective of causality, need to be reported. Any ongoing SAEs, AESIs, or treatment-related Grade 3/4 AEs will be followed until resolution or stabilization or until loss to follow-up. AEs and laboratory abnormalities will be graded according to the NCI CTCAE grading system (v5.0) and recorded on the eCRF.

Complete details for monitoring AEs, including the definition of drug-related AEs, are provided in [Section 8](#).

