## 8.8 Recording of Adverse Events, Serious Adverse Events, and Adverse Events of Special Interest

Events that occur after signing of informed consent but prior to initiation of study drug, unless due to a protocol-mandated procedure, will be recorded on the Medical History eCRF. Any AE that occurs after first dose of study drug through 28 days after receiving the last dose of oral study drug or 100 days after receiving the last dose of IV study drug, whichever occurs later, will be recorded on the AE eCRF. After the 28-day or 100-day reporting window after discontinuation of treatment, only SAEs assessed as related to study drug and all AESIs, irrespective of causality, need to be reported. Information on the follow-up of AEs, SAEs, and AESIs is provided in [Section 8.9](#).

In order to avoid vague, ambiguous, or colloquial expressions, the AE should be recorded in standard medical terminology rather than the patient's own words. Whenever possible, the investigator should combine signs and symptoms that constitute a single disease entity or syndrome into a final diagnosis, if appropriate. For example, fever, cough, and shortness of breath may be reported as pneumonia, if that is a reasonable diagnosis.

Each AE is to be evaluated for **causal relationship** to the investigational drug, severity, and, seriousness. The action taken, and the outcome must also be recorded.

SAEs and AESIs that occur during the study or within 28 days after receiving the last dose of oral study drug or 100 days after receiving the last dose of IV study drug, whichever is later, whether or not related to study drug, must be reported immediately (ie, **within 24 hours** of knowledge of the event or additional information for a previously reported event) to the sponsor/SAE designee. The contact information for reporting of SAEs/AESIs can be found on the SAE/ AESI Reporting Form.

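### The planned cumulative incidence of first dose-changing adverse event uses only patients who had the event, so it always ends at 100% and shows onset time among affected patients, not incidence

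*Combined protocol and SAP*

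**What the plan says.** Section 9.8.1 defines a time-to-first-event variable for the first TEAE, and for the "first treatment-related TEAE that results in a dose reduction, delay, interruption or discontinuation of study drug". Time runs from first dose to the start of that event, plus one day. The section then says: "The cumulative incidence is presented in a 1-KM graph for just the patients with an event", and adds a median time to onset with a 95% CI. It gives no censoring date for patients who never have the event.

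Later in the same section, after listing combined preferred terms, the plan says that "the analysis of combined terms for anemia is explored as a time to first event analysis as described above".

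The surrounding rules are these:

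- **Section 9.8:** "Safety endpoints are incidence of AEs, clinical laboratory abnormalities, and dose modifications". It also says that the safety analyses take in everyone who received at least one dose of either drug.
- **Section 9.3:** "The Safety Population will consist of all patients who received at least 1 full or partial dose of any protocol-specified treatment".
- **Section 9.1:** time-to-event variables are summarized by Kaplan-Meier, with both the number of events and the number censored reported. Further detail is left to a SAP.
- **Section 9.4:** the size of each analysis population is reported.
- **Section 9.8.1, table list:** separate tables, all-cause and treatment-related, for TEAEs leading to discontinuation, to interruption or delay, and to dose reduction. The list is open-ended.

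**The concern.** A cumulative incidence is the share of the patients at risk who have had the event by a given time, so its denominator must include those who never have it. The planned curve removes exactly those patients. What remains answers a different question: among patients who had the event, how early did it come?

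Dose modification is a named safety endpoint, and safety and tolerability of the combination is a secondary objective. A figure headed cumulative incidence would be read as the risk of a dose-changing event over time, and its height carries no information about that risk. The median has the same limit: half of affected patients had onset by that day, which is not the day by which half of treated patients were affected.

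**Working it through.** The plan states no figure for this analysis, so there is nothing to reproduce. The check is the algebra of the estimator, followed by an illustration.

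**Inputs from the document.** Cohort sizes are 43 (Cohort A1 maximum) and 10 (Cohort A2), from the synopsis and Section 4.1. The analysis set for the curve is patients with the event only (Section 9.8.1).

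**Assumed inputs.** The document gives no event counts or onset times. I take 20% to 90% affected, onsets evenly spaced over days 8 to 120, and unaffected patients followed beyond the last onset.

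**Step 1: events-only curve.** Let k patients have the event. All k have an observed time and none is censored, so

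1 − S(t) = (number of onsets by t) / k.

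At the last onset this is k/k = 1. It holds for any k ≥ 1, any cohort size and any onset pattern, and needs none of the assumptions above.

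**Step 2: all treated patients.** With n treated and no loss before the last onset,

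1 − S(t) = (number of onsets by t) / n,

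which ends at k/n.

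| n | k | Events-only end | Events-only median | All-treated end (k/n) | All-treated median |
|---|---|---|---|---|---|
| 43 | 9 | 100% | day 64 | 20.9% | not reached |
| 43 | 13 | 100% | day 64 | 30.2% | not reached |
| 43 | 22 | 100% | day 61 | 51.2% | day 120 |
| 43 | 30 | 100% | day 62 | 69.8% | day 89 |
| 43 | 39 | 100% | day 64 | 90.7% | day 70 |
| 10 | 2 | 100% | day 8 | 20.0% | not reached |
| 10 | 5 | 100% | day 64 | 50.0% | day 120 |
| 10 | 9 | 100% | day 64 | 90.0% | day 64 |

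The rows for 13 and 39 affected make the point: a threefold difference in incidence (39/13 = 3) leaves both the end of the events-only curve and its median unchanged.

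**Step 3: staggered follow-up.** I simulated 43 patients 1,000 times, with exponential onset and censoring uniform over days 60 to 700 (both assumed).

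| True one-year incidence | Events-only curve at day 365 | All-treated 1-KM at day 365 |
|---|---|---|
| 30% | 81.6% | 29.8% |
| 50% | 85.9% | 50.0% |
| 70% | 90.3% | 69.7% |

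**Step 4: why a competing-event rule is needed.** Restoring the unaffected patients is not enough if those who stop treatment or die without the event are simply censored. Assume 43 treated, 15 events and 20 treatment ends without the event, both spread evenly over 12 months, and 8 patients followed to month 25. Censoring at treatment end gives 1-KM = 51.2%. Aalen-Johansen, with treatment end as competing, gives 34.9% = 15/43.

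**Step 5: consistency with the plan's own rules.** Section 9.8 brings all treated patients into the safety analyses, but this curve leaves out the unaffected. Section 9.1 asks for the number censored, which is zero by construction here. In the anemia sentence, the reference back to the method just described most naturally brings the restriction with it.

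**The case against.** The strongest reply is that the restriction is disclosed in the same sentence, and that median time to onset is a fair name for a conditional quantity. A reader who takes in the whole sentence is not deceived, and the error comes down to the words cumulative incidence. That much stands, and it limits the severity. It does not make the label right: a figure is often read apart from its methods text, and this one cannot show an incidence.

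It can also be said that incidence over time is not itself a named endpoint, and that a whole-cohort curve in cohorts of 10 and 18 to 43 is a reviewer's preference. This is fair as regards the choice of Aalen-Johansen, and it is why relabelling is an acceptable minimum. But the plan itself chose to present a cumulative incidence, and what it specifies is not one.

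Two stronger readings are tempting, and the document does not support them.

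- **That the share affected would be nowhere available.** Section 9.1 requires the number of events for time-to-event variables and Section 9.4 the population sizes, so affected/treated can be derived for the plotted endpoint. Section 9.8.1 also tabulates crude incidence by type of dose change. For anemia, incidence is available from the preferred-term and combined-term summaries.
- **That the curves would put the two cohorts in the wrong order.** This can be produced only by choosing different onset spreads for the two cohorts. The cohorts are summarized separately, and no cross-cohort safety comparison is planned.

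**Conclusion.** The analysis is wrong as written, and the consequence is limited. The events-only 1-KM curve ends at 100% in every case, so it is mislabelled as a cumulative incidence, and its median and CI apply only to patients who had the event. This conclusion is algebraic and rests on no assumption. The size of any misreading does depend on assumptions: over the range of 20% to 90% affected, reading the end of the curve as incidence would overstate it by 80 to 10 percentage points (100 − 20 to 100 − 90).

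The display is descriptive. The primary ORR analysis, the Simon Stage 1 decision and the crude safety tables are untouched. That the anemia analysis is affected rests on the natural reading of its cross-reference, since the text does not say so outright. The document leaves further detail to a SAP and contains no later text that corrects the point.

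**What to change.** **Preferred.** Estimate the cumulative incidence in all treated patients of each cohort (the Safety Population), keeping patients without the event in the risk set. State the censoring rule. Treat death, and end of study treatment without the event, as competing events, for instance with Aalen-Johansen.

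**Minimum.** Keep the events-only plot and median, title both *time to onset among patients with the event*, and print the number affected out of the number treated beside them. This removes the mislabelling but gives no incidence over time.

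State the same choice explicitly for the combined anemia terms.

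**Cost.** The preferred version needs a few lines of SAP wording and a small amount of programming, and no new data for the dose-change events. The minimum costs almost nothing.
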